# 1.0 TRIAL SUMMARY

Abbreviated Title	A phase I/II study of pembrolizumab and vorinostat in patients with immune therapy naïve and immune therapy pretreated Stage IV NSCLC		
Trial Phase	1/11		
Clinical Indication	Stage IV NSCLC, ECOG 0-1 patients who are immunotherapy naïve and immune- therapy pretreated. Second line or greater.		
Trial Type	phase I/randomized phase II		
Type of control	Pembrolizumab for the randomized phase II portion.		
Route of administration	Pembrolizumab IV		
	Vorinostat PO		
Trial Blinding	Open Label		
Treatment Groups	Phase I: Vorinostat dose escalation.		
	Phase Ib: Vorinostat Ib expansion.		
	Randomized Phase II: Arm A (pembrolizumab alone), Arm B (pembrolizumab plus vorinostat).		
Number of trial subjects	Total=108		
	Phase I dose escalation: 12		
	Phase lb: 18		
	Randomized phase II: 78		
Estimated enrollment period	18 months		
Estimated duration of trial	24 months		
Duration of Participation	24 months		

#### 2.0 TRIAL DESIGN

#### 2.1 Trial Design

We propose a phase I/randomized phase II clinical trial of pembrolizumab and vorinostat in ECOG 0-1 patients with immune therapy naïve and immune therapy pretreated locally advanced or metastatic NSCLC who have progressed through one prior line of therapy (**Figure 1**). The study would begin with a phase I dose escalation utilizing the modified continuous reassessment method (O'Quigley, Pepe, & Fisher, 1990). This would be followed by a phase I expansion at the maximum tolerated dose (MTD) in 18 NSCLC patients who have been previously treated with anti-PD-1 or anti-PD-L1 therapy. In parallel, a separate phase II arm will randomize 78 patients to a pembrolizumab alone group and a pembrolizumab plus vorinostat group.

# 2.2 Trial Diagram

[figure not shown]

Figure 1. Clinical trial schema. \*Pre-treatment and post-treatment biopsies will be obtained in both the phase Ib expansion and the randomized phase II patients. R (Randomization), P (Pembrolizumab), V (Vorinostat), MTD (maximum tolerated dose).

#### 3.0 OBJECTIVES & HYPOTHESES

## 3.1 Primary Objectives & Hypotheses

#### Phase 1 Escalation:

**Primary Objective:** To determine the safety, tolerability and feasibility of concurrent administration of vorinostat and Pembrolizumab.

*Hypothesis:* Concurrent administration of vorinostat and Pembrolizumab will be safe, tolerable, and feasible.

#### Phase 1b Expansion (Single Arm, Pre-treated Cohort):

**Primary Objective:** To determine whether concurrent administration of vorinostat and Pembrolizumab will be effective in NSCLC patients who have been previously exposed to anti-PD-1 or anti-PD-L1 therapy.

*Hypothesis:* Concurrent administration of vorinostat and Pembrolizumab will be effective in NSCLC patients who have been previously treated with anti-PD-1 or anti-PD-L1 therapy.

## Phase II (Randomized, Treatment Naïve Cohort):

**Primary Objective:** To determine whether concurrent administration of vorinostat and Pembrolizumab is more effective than Pembrolizumab alone.

*Hypothesis:* Concurrent administration of vorinostat and Pembrolizumab will result in a higher response rate and progression-free survival (PFS) than Pembrolizumab alone.

# 3.2 Secondary Objectives & Hypotheses

#### Secondary Objectives (Phase 1 expansion and phase II Arms A and B):

- 1. To determine immunogenicity molecular profiles that correlate with outcome measures.
- 2. To determine immunogenicity profiles that correlate with resistance to therapy.
- 3. To examine and model the mechanisms of resistance to immunotherapy available to cancer cells and the eco-evolutionary dynamics that govern proliferation of the resistant phenotypes.

#### Secondary Hypotheses (Phase 1 expansion and Phase II Arms A and B):

- 1. High immunogenicity (High-IG) profiles in pre-treatment biopsies will predict for anti-PD-1+/-vorinostat responsiveness in the Phase I expansion cohort.
- 2. High or Low immunogenicity (High/Low-IG) profiles will result in a higher response rate in the anti-PD-1+vorinostat therapy group than in the anti-PD1 treatment alone

group in the phase II cohort.

3. During/Post-treatment biopsies we will find that vorinostat combined with anti-PD1 treatment will enhance IG profiles compared to anti-PD1 treatment alone in the Phase I expansion cohort and the phase II cohort.

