#### 8.7.1 Statistical plan for immunogenicity profiles in phase Ib and phase II:

# Phase Ib expansion cohort (PD-1 pretreated: N=18).

Two gene signatures (NF-kB, 12-chemokine genes) will be evaluated to test if they can predict the response to PD-1 blockade + HDACi treatment using the pre-treatment biopsy. For each gene signature, PCA will be used to calculate an index score based on the first principal component. The derived gene signature score will be then used to test if the response group has a higher score than the non-response group using the two-sample t test. A sample size of 18 patients will give an 80% power to detect an effect size of 1.6 with a two-sided 5% type error if the response rate is 30% (i.e., 5 responders and 13 non-

responders) by the two-sample t test. If the response rate is 40% (i.e., 7 responders and 11 non-responders), the power will increase to 87%. We will also test the difference of the score from pre to post-treatment between the responders and non-responders using two-sample t-test. With this sample size (n=18) and 80% power, it will be able to detect an effect size of 1.57 and 1.45 for a response rate of 30% and 40%, respectively with a two-sided 5% type error by the two-sample t-test. In addition, we will also determine association of individual genes with response or resistance, including T cell co-stimulatory and inhibitory genes.

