#### Phase II cohort (PD-1 naïve).

We would like to know if these gene signatures in pre-treatment biopsies could predict a differential treatment effect. That is, could patients with high gene signature score result in a higher response rate to anti-PD-1 but patients with either low or high respond to anti-PD-1+HDACi? A logistic regression model will be used to evaluate this hypothesis by testing an interaction effect model, which includes two main effects, gene signature score and treatment status, and their interaction term. We will also test the difference of the score from pre to post-treatment between the two treatment groups using two-sample t-test.

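### Secondary hypothesis 3 compares with anti-PD-1 alone in a phase Ib cohort that has no such arm; the valid phase II test would be more precise with baseline adjustment

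*Combined protocol and SAP*

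**What the plan says.** Hypothesis 3 in section 3.2 concerns biopsies taken during or after treatment. It expects vorinostat plus anti-PD-1 to enhance immunogenicity profiles "compared to anti-PD1 treatment alone in the Phase I expansion cohort and the phase II cohort".

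Section 3.1 heads the expansion cohort "Phase 1b Expansion (Single Arm, Pre-treated Cohort"), and its main aim there is "To determine whether concurrent administration of vorinostat and Pembrolizumab will be effective in NSCLC patients who have been previously exposed" (the earlier exposure being to a PD-1 or PD-L1 antibody). Section 2.1 describes it as a "phase I expansion at the maximum tolerated dose (MTD) in 18 NSCLC patients". Sections 4.2.2 and 5.2 have pembrolizumab and vorinostat begin together on cycle 1 day 1, with no pembrolizumab-only lead-in. The one pembrolizumab-alone group is in section 1.0: "Randomized Phase II: Arm A (pembrolizumab alone), Arm B (pembrolizumab plus vorinostat").

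Section 8.7.1 gives the analyses of signature change. For phase Ib it tests the "difference of the score from pre to post-treatment between the responders and non-responders". For phase II it says: "We will also test the difference of the score from pre to post-treatment between the two treatment groups using two-sample t-test". The phase II test has no covariates and no stated power. Randomization is stratified by histology and PD-L1 level (section 5.4).

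**The concern.** The hypothesis names a contrast, combination versus anti-PD-1 alone, in two cohorts, and only one of them contains both sides of it. In phase Ib, any rise from the pre-treatment to the on-treatment biopsy is the joint effect of pembrolizumab and vorinostat (plus time and regression to the mean). The vorinostat share cannot be separated out. Of the 18 patients, none belongs to a concurrent anti-PD-1-alone group. If the sentence stays as it is, the trial has half a secondary hypothesis that no analysis in section 8.7.1 addresses, and a favourable phase Ib change could be cited under it.

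That makes the phase II comparison the only test of the hypothesis, so its precision matters. On-treatment biopsies are taken only where feasible (section 6.1, footnote b), and section 8.2.5 plans no handling of missing values. An analysis that gets less from each available pair has a cost here, and the adjusted alternative needs no new data.

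**Working it through.** **Phase Ib: is the contrast identifiable?**

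- Arms: one (section 3.1). Treatment: both drugs from cycle 1 day 1 (sections 4.2.2, 5.2).
- Samples: one biopsy before treatment and one at cycle 1 days 15–21 (section 4.3.4.1).
- Planned contrast for change: responders versus non-responders (section 8.7.1).

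The responder contrast asks whether change tracks outcome among patients who all take vorinostat, so it carries no information on vorinostat versus none. Phase II Arm A is not a usable substitute control. Phase II excludes prior checkpoint therapy and phase Ib requires it (section 5.1.3, items 5 and 6). Phase II also requires a PD-L1 score of at least 1% and, with exceptions, no prior treatment in the stage IV setting (section 5.1.2, items 6 and 11). The plan does not propose such a comparison.

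**The plan's own change-score figures.** Section 8.7.1 gives detectable effects of 1.57 (5 versus 13) and 1.45 (7 versus 11) for the phase Ib responder contrast, at 80% power and two-sided 5%. Noncentral-t power with n1+n2−2 degrees of freedom gives 1.571 and 1.443, so these reproduce. They do not bear on hypothesis 3, for which no power figure is given.

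**Phase II: change score versus baseline adjustment.** Let the score have SD s1 before and s2 on treatment, with within-arm correlation rho. Per-patient variance entering the arm difference:

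- Change score: s1² + s2² − 2·rho·s1·s2
- Adjusted for baseline (ANCOVA): s2²(1 − rho²)
- Excess of the first over the second: (s1 − rho·s2)² = s1²(1 − b)², where b = rho·s2/s1 is the slope on baseline

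The excess is never negative and is zero when b = 1. With s1 = s2 = s, the variances are 2(1 − rho)s² and (1 − rho²)s², and the ratio of adjusted to change-score variance is (1 − rho²)/(2(1 − rho)) = (1 + rho)/2.

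Rho and the SDs are not in the documents, so equal SDs are assumed and rho is varied. The detectable effects and powers also assume 39 complete pairs per arm (the maximum in section 8.2.6) and a two-sided 5% level, which is stated for phase Ib but not for this test. At 39 per arm, 80% power requires 0.643 SD of the analysed quantity. Multiplying by √(2(1 − rho)) or √(1 − rho²) gives raw-score SD units.

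| rho | Variance ratio | Detectable effect, change / adjusted | Power at 0.64 raw SD, change / adjusted |
|---|---|---|---|
| 0 | 50% | 0.91 / 0.64 | 51% / 80% |
| 0.3 | 65% | 0.76 / 0.61 | 65% / 83% |
| 0.5 | 75% | 0.64 / 0.56 | 80% / 90% |
| 0.7 | 85% | 0.50 / 0.46 | 95% / 97% |
| 0.9 | 95% | 0.29 / 0.28 | above 99% / above 99% |

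Simulation with 39 per arm (4000 runs) gave 65% / 82%, 80% / 90% and 96% / 97% at rho 0.3, 0.5 and 0.7.

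**How firm is 39 per arm?** In the section 8.7 table for scenario 1, Arm A fails stage 1 with probability 0.01 + 0.04 + 0.43 = 0.48, which leaves it at 23 patients. Fewer pairs raise the effect detectable by the change score from 0.643 to 0.78 SD of change with an assumed 27 pairs per arm, and to 0.85 with 23 per arm. The variance ratio does not depend on the number of pairs.

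**The case against.** The strongest reply is that nothing planned is invalid. The mismatch sits in one sentence of section 3.2. Section 8.7.1 tests the vorinostat increment only in phase II, where it belongs, and a t-test on change is a legitimate randomized comparison for a secondary correlative endpoint with no stated power. That stands. Preferring adjustment is a matter of efficiency, and its size rests on an undocumented rho and on equal variances. At rho 0.7 or above the gain is small.

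A reader might infer four stronger things that the documents do not support:

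- *The phase II test ignores the baseline, or is biased.* The change score subtracts each patient's baseline, which is adjustment with a coefficient fixed at 1, and under randomization it is unbiased.
- *The plan will report phase Ib as a vorinostat effect.* No such analysis is specified. The risk comes from the wording of the hypothesis.
- *No within-patient change is examined.* Section 4.3.4, under pharmacodynamic studies, plans to look at treatment-related change in immune cell presence by IHC and at pre- and post-treatment histone acetylation. What is missing is a named test of mean change in the signature score.
- *No phase Ib specimen could follow anti-PD-1 without vorinostat.* Prior checkpoint therapy is required and the baseline specimen must post-date the latest treatment, so some may. They are still not a concurrent control: the last line may have been another drug, and antibodies within 4 weeks are excluded (section 5.1.3, item 9).

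None of this gives phase Ib an anti-PD-1-alone arm, and no section resolves the mismatch.

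**Conclusion.** The phase Ib half of hypothesis 3 cannot be tested as worded. This follows from the design alone and rests on no numerical assumption. The planned responder contrast does not repair it.

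The phase II half is testable and the planned test is sound, but it is less precise than a baseline-adjusted model unless the slope on baseline is near 1. With equal variances the adjusted variance is 50% to 95% of the change-score variance for rho from 0 to 0.9, equivalent to needing 50% to 5% fewer pairs for the same power. This is a loss of precision in a secondary analysis. It affects neither validity nor the primary response-rate comparison. Any further gain from the stratification factors is not quantified here.

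**What to change.** - Section 3.2, hypothesis 3: limit the comparison with anti-PD-1 alone to the phase II cohort.
- Sections 3.2 and 8.7.1, phase Ib: state the hypothesis as a within-patient increase in signature score from the pre-treatment to the on-treatment biopsy. Test it with a paired comparison and report it as the effect of the combination. The responder contrast can stay as a separate question.
- Section 8.7.1, phase II: replace the change-score t-test with a linear model of the on-treatment score on arm, baseline score, histology and PD-L1 level. Report the number of complete pairs per arm.

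The cost is wording in two sections. The biopsies, assays and sample size are unchanged. The model uses a few degrees of freedom, which is minor at 39 pairs per arm and somewhat less so at 23. Phase Ib gives up a vorinostat-specific claim that its design could not support.

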#### 4.0 BACKGROUND & RATIONALE

## 4.1 Background

Refer to the Investigator's Brochure (IB)/approved labeling for detailed background information on pembrolizumab.

# 4.1.1 Pharmaceutical and Therapeutic Background

The importance of intact immune surveillance in controlling outgrowth of neoplastic transformation has been known for decades. Accumulating evidence shows a correlation between tumor-infiltrating lymphocytes (TILs) in cancer tissue and favorable prognosis in various malignancies. In particular, the presence of CD8+ T-cells and the ratio of CD8+ effector T-cells / FoxP3+ regulatory T-cells seems to correlate with improved prognosis and long-term survival in many solid tumors.

The PD-1 receptor-ligand interaction is a major pathway hijacked by tumors to suppress immune control. The normal function of PD-1, expressed on the cell surface of activated Tcells under healthy conditions, is to down-modulate unwanted or excessive immune responses, including autoimmune reactions. PD-1 (encoded by the gene Pdcd1) is an Ig superfamily member related to CD28 and CTLA-4 which has been shown to negatively regulate antigen receptor signaling upon engagement of its ligands (PD-L1 and/or PD-L2). The structure of murine PD-1 has been resolved. PD-1 and family members are type I transmembrane glycoproteins containing an lg Variable-type (V-type) domain responsible for ligand binding and a cytoplasmic tail which is responsible for the binding of signaling molecules. The cytoplasmic tail of PD-1 contains 2 tyrosine-based signaling motifs, an immunoreceptor tyrosine-based inhibition motif (ITIM) and an immunoreceptor tyrosinebased switch motif (ITSM). Following T-cell stimulation, PD-1 recruits the tyrosine phosphatases SHP-1 and SHP-2 to the ITSM motif within its cytoplasmic tail, leading to the dephosphorylation of effector molecules such as CD3ζ, PKCθ and ZAP70 which are involved in the CD3 T-cell signaling cascade. The mechanism by which PD-1 down modulates T-cell responses is similar to, but distinct from that of CTLA-4 as both molecules regulate an overlapping set of signaling proteins. PD-1 was shown to be expressed on activated lymphocytes including peripheral CD4+ and CD8+ T-cells, B-cells, T regs and Natural Killer cells. Expression has also been shown during thymic development on CD4-CD8- (double negative) T-cells as well as subsets of macrophages and dendritic cells. The ligands for PD-1 (PD-L1 and PD-L2) are constitutively expressed or can be induced in a variety of cell types, including non-hematopoietic tissues as well as in various tumors. Both ligands are type I transmembrane receptors containing both IgV- and IgC-like domains in the extracellular region and contain short cytoplasmic regions with no known signaling motifs. Binding of either PD-1 ligand to PD-1 inhibits T-cell activation triggered through the T-cell receptor. PD-L1 is expressed at low levels on various non-hematopoietic tissues. most notably on vascular endothelium, whereas PD-L2 protein is only detectably expressed on antigen-presenting cells found in lymphoid tissue or chronic inflammatory environments.

PD-L2 is thought to control immune T-cell activation in lymphoid organs, whereas PD-L1 serves to dampen unwarranted T-cell function in peripheral tissues. Although healthy organs express little (if any) PD-L1, a variety of cancers were demonstrated to express abundant levels of this T-cell inhibitor. PD-1 has been suggested to regulate tumor-specific T-cell expansion in subjects with melanoma (MEL). This suggests that the PD-1/PD-L1 pathway plays a critical role in tumor immune evasion and should be considered as an attractive target for therapeutic intervention.

Pembrolizumab is a potent and highly selective humanized monoclonal antibody (mAb) of the IgG4/kappa isotype designed to directly block the interaction between PD-1 and its ligands, PD-L1 and PD-L2. KeytrudaTM (pembrolizumab) has recently been approved in the United Stated for the treatment of patients with unresectable or metastatic melanoma and disease progression following ipilumumab and, if BRAF V600 mutation positive, a BRAF inhibitor.

#### 4.1.2 Preclinical and Clinical Trial Data

Refer to the Investigator's Brochure for Preclinical and Clinical data.

#### 4.2 Rationale

# 4.2.1 Rationale for the Trial and Selected Subject Population

The World Health Organization estimated that 1.6 million people died of lung cancer in 2012 (Ferlay et al., 2014). Phase I clinical trials have shown that antibody mediated blockade of either PD-L1 or PD-1 can lead to durable tumor regression in about 20% of patients with advanced non-small cell lung cancer (NSCLC) (Brahmer et al., 2012; Edward B Garon, 2013, 2014; Ghandi, 2014; Suzanne L. Topalian et al., 2012). The pre-clinical and clinical data outlined below indicate that histone deacetylase inhibitors (HDACi) may enhance the efficacy of immune checkpoint inhibition (Juergens et al., 2011; Kelly et al., 2005; Kelly et al., 2003; Ma et al., 2013; Schrump et al., 2008; Vansteenkiste et al., 2008; Wrangle, 2013; Wrangle et al., 2013).

#### Pembrolizumab (MK3475; Keytruda) in Lung Cancer.

Many studies have evaluated the PD-1/PD-L1 inhibitors in the treatment of advanced stage NSCLC. In summary, overall response rates were ~18% with indications that (1) responses were durable and (2) PD-L1 positivity played a role in response (Brahmer et al., 2012; S. L. Topalian et al., 2012). Immune-related toxicities were seen with both compounds, including pneumonitis at a rate of 3% with the PD-1 inhibitor (Brahmer et al., 2012). Most of these adverse events improved with drug cessation and treatment with glucorticocorticoids/endocrine therapy replacement where appropriate.

In October 2013 and April 2014, respectively, [name] et al. and [name] et al. presented the results of a phase I study of pembrolizumab (PD-1 inhibitor) in patients with advanced stage NSCLC refractory to 2 lines of prior treatment (Edward B Garon, 2013; Ghandi, 2014). Thirty-eight patients were enrolled. The overall objective response rate was 24% using investigator-assessed immune-related response criteria (irRC). Six of 9 (67%, 95% CI 30-93%) patients with PD-L1 high tumors responded to therapy versus 0/22 (0%, 95% CI 0-15%) patients with PD-L1 low tumors. The most common drug-related adverse

events were rash, pruritus, and fatigue (16% each), and diarrhea (13%). The only grade 3/4 event was one patient who developed grade 3 pulmonary edema. There were no drug-related deaths.

In June 2014, [name] et al. presented preliminary results from KENOTE-001, a phase I study that randomized 217 patients with known PD-L1 status to pembrolizumab 10mg/kg every 2 weeks (Q2W) and pembrolizumab 10mg/kg every 3 weeks (Q3W) (Edward B Garon, 2014). The overall response rate (ORR) in all patients was 18% (95% CI 13-24%) by irRC and 20% (95% CI 15-26%) by RECIST v1.1. Patients with PD-L1 expressing tumors had ORR of 19% (95% CI 14-26%) by irRC and 23% (16-30%) by RECIST. Patients with PD-L1 negative tumors had ORR of 13% (95% CI 4-27%) by irRC and 9% (2-23%) by RECIST. At the interim analysis, there was no statistical difference in response rates in the different dosage groups. The most common drug—related adverse events included fatigue (13%), decreased appetite (6.5%), arthralgia (6.1%), pruritis (5.4%), and pyrexia (3.6%) and most of these were grade 1/2. Six percent of patients had grade 3/4 drug-related adverse events. Four patients (2 patients in each schedule) developed grade 3/4 pneumonitis.

Updated results of KEYNOTE-001 were recently published by Garon et al. and showed that the objective response rate among all patients was 19.4% (95% CI, 16.0-23.2) and the median duration of response was 12.5 months (range, 1.0-23.3), median PFS 3.7 months (95% CI, 2.9-4.1), and OS 12.0 months (95% CI, 9.3-14.7)(E. B. Garon et al., 2015). The response rate in patients with at least 50% of tumor cells staining positive for PD-L1 was 45.2% (95% CI, 33.5-57.3), median PFS 6.3 months (95% CI, 2.9-12.5), and median OS was not reached (95% CI, 13.7 to not reached). PD-L1 expression in at least 50% of tumor cells correlated with better efficacy of pembrolizumab; however, it is important to note that 16.5% (95% CI, 9.9-25.1) of patients with 1-49% PD-L1 staining responded and 10.7% (95% CI, 2.3-28.2%) of patients with <1% PD-L1 staining also responded. Of the 42 patients treated in the first-line setting, those with a TPS of 1-49%, 5/26 (19.2%) achieved an ORR while in the TPS ≥ 50% group, 8/16 (50%) achieved and objective response. Pembrolizumab was FDA approved in 2016 for first-line NSCLC PD-L1 ≥50 %.

The phase 1/2 KEYNOTE 021 study comparing pembrolizumab plus chemotherapy to pembrolizumab alone was recently presented at ESMO 2016. It demonstrated an improvement in OS and PFS of the triplet compared to the doublet (Langer et al, ESMO 2016). Based on these results carboplatin, pemetrexed plus pembrolizumab was submitted to the FDA as a regimen for first line, Non-squamous NSCLC regardless of PDL1 status.

